Level two allocation involves the randomisation of young people to RBT or BAU. This will be conducted by research staff, using a secure, on-line randomisation service (Sealed Envelope Ltd). after informed consent has been taken and the baseline assessment completed and before any trauma screening has been conducted. The allocation will involve an equal probability of receiving RBT or BAU and will employ random permuted blocks of variable size (4, 6 or 8) with a random block seeded throughout. Randomisation will be conducted by research staff using a secure, independent randomisation service, Sealed Envelope Ltd. Randomisation will be stratified by service (youth justice, edge of care, youth development, early help, children's services), sex (male, female), and age group (<15 years, 15 years or more). Stratification variables have been chosen to ensure allocation is balanced across services, sex, and age as some workers specialise in working with older or younger males and females. A full quality assurance AUDIT trail will be kept of all allocations and research staff will not be able to see future allocations. The allocated group will be relayed back to delivery staff in the services who will decide which staff member, matching their allocated intervention or control group, a young person should be assigned to.

It is not possible to blind young people or staff to their allocated group although follow-up at months 6 and 12 will be conducted by researchers blind to allocation. Follow-up questionnaires are completed by participants and are the same for both groups, the questionnaires collect no details on what group the participant was allocated to.

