### **Sample size calculations**

Sample size calculations were derived using Stata 16 and are based on the Self-Report Delinquency Scale (Smith and McVie, 2003). This measure has 18 two-part questions that measure the number of different offences committed, and the volume of offences committed

over a fixed period. We are interested in the latter outcome over a six-month period. The scale has good psychometric properties (Fonagy et al., 2018, Humayun et al., 2017) and correlates well with official police charges ( $R = 0.95$ ; (McAra and McVie, 2007)).

We have used an effect size difference of 0.25 as an important difference; this equates to a difference in volume of offences of circa 12% over a 6-month period, similar effects as found in other psychologically focussed interventions to reduce recidivism in adolescent populations (Hodgkinson et al., 2021). To detect this difference or greater, using a two-sided test, alpha of 0.05 and power at 80% requires 506 young people to be followed-up at our primary endpoint, 6-months post-randomisation, 253 in each group. There is no reliable literature on pre- and post-test correlations for the SRDS, so we have erred on the side of caution and not accounted for this in the sample size calculation as an incorrect assumption increases the risk of an under-powered trial. If we take a potential loss to follow-up of 10%, similar to attrition found in our other studies of young people (Coulton S et al., 2023), this inflates the required baseline sample to 562. We have 80 potential interventionists, 40 randomised to each arm. Each interventionist can manage a harmonic mean of 10 young people through the course of the study. To achieve our target, we would need to have at least 56 of these interventionists participating throughout the trial, 28 in each arm, thus allowing for a potential loss of interventionists of 24, 30% of those available.

Assuming only 80% of young people approached consent to take part, as found in similar studies (Coulton S et al., 2023), means we would need to approach 702 young people, over the recruitment period. Allowing for a slower start of 20/ per month recruited over the first three months, means 36 will need to be recruited in each month between January 2024 and February 2025, allowing for a six-month follow-up for the interim report submitted in September 2025.

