### **Analysis**

The proposed analysis is covered in depth in the associated statistical analysis plan.

Objective 1: Participant flow through the study will be presented as a CONSORT diagram. We will present demographics and outcome variables for each group at each time-point. We will explore the validity of the randomisation procedure by presenting baseline outcomes and estimates of precision by allocated group.

Objective 2: The primary outcome is the mean difference between BAU and RBT in number of offences over the 6 months from baseline, assessed using the SRDS at 6-months. The analysis will be conducted using an analysis by intention to treat (ITT) and will include all available data with participants maintained as members of their allocated group, irrespective of whether they complied with the intervention or not. Data will be assessed for distributional assumptions and will probably take the form of a generalised linear regression model, adjusted for baseline stratification covariates and baseline SRDS score. Both the intervention and control vary by service, with a higher to lower hierarchy of complexity running from youth justice, edge of care, children's services, youth development to early help. What is delivered in both the intervention and control group is tailored to the young person's needs. While we

can describe the variety of different sessions delivered in our results, we cannot completely account for it in the analysis, nor can we adjust for any potential contamination due to multi-agency working. Instead, we take a holistic approach, seeing what is delivered as a whole, rather than the sum of its individual parts. Though as complexity is hierarchical across services, we will adjust the analysis for service. This provides the best estimate of effect of how the intervention is proposed to be implemented across diverse services and as a rigorously designed RCT any potential errors introduced will be equally distributed across both groups and mitigated in the analysis. We will apply a multi-level model allowing for participants to be nested within services as a fixed effect. Results will be presented as a mean difference and associated 95% confidence intervals. A secondary analysis will be conducted using a similar approach at month 12.

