The efficacy trial design is a mixed method, two level, individually randomised controlled trial of a trauma informed intervention, Trauma Recovery Model Relationship Building Together (RBT), versus business as usual (BAU) for adolescents and young adults served by Bridgend Youth Services (youth justice, edge of care, youth development and early help). There are two levels to the study randomisation. Level one involves selecting staff to be trained in RBT. This allocation is done for all staff, after baseline staff data collection, and is conducted by an on-line independent secure randomisation service, Sealed Envelope Ltd. Consent will be sought from all eligible staff prior to randomisation. As allocations are done at the same time and because we want to maximise balance across the groups on key parameters, we will employ minimisation for the allocation of staff. Our aim will be to maximise balance in terms of service (youth justice, edge of care, children's services, youth development, and early help) and speciality (specialised staff versus generic staff). Provision has been made to conduct a second wave of staff randomisation and TRM training if there is a high turnover of staff throughout the trial – a high turnover is one that exceeds 30%.

Level two allocation involves the randomisation of young people to RBT or BAU. This will be conducted by research staff, using a secure, on-line randomisation service (Sealed Envelope Ltd). after informed consent has been taken and the baseline assessment completed and before any trauma screening has been conducted. The allocation will involve an equal probability of receiving RBT or BAU and will employ random permuted blocks of variable size (4, 6 or 8) with a random block seeded throughout. Randomisation will be stratified by service (youth justice, edge of care, children's services, youth development and early help), sex (male, female), and age group (<15 years, 15 years or more). Stratification variables have been chosen to ensure allocation is balanced across services, sex, and age as some workers specialise in working with older or younger males and females.

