We have used an effect size difference of 0.25 as an important difference; this equates to a difference in volume of offences of circa 12% over a 6-month period, similar effects as found in other psychologically focussed interventions to reduce recidivism in adolescent populations (Hodgkinson et al., 2021). To detect this difference or greater, using a two-sided test, alpha of 0.05 and power at 80% requires 506 young people to be followed-up at our primary endpoint, 6-months post-randomisation, 253 in each group. There is no reliable literature on pre- and post-test correlations for the SRDS, so we have erred on the side of caution and not accounted for this in the sample size calculation as an incorrect assumption increases the risk of an under-powered trial. If we take a potential loss to follow-up of 10%, similar to attrition found in our other studies of young people (Coulton S et al., 2023) this inflates the required baseline sample to 562. We have 73 potential interventionists, 35 randomised to control and 36 randomised to be trained in the intervention delivery. Each interventionist can manage a harmonic mean of 10 young people through the course of the study. To achieve our target, we would need to have at least 56 of these interventionists participating throughout the trial, 28 in each arm, thus allowing for a potential loss of interventionists of 17, 23% of those available.

Assuming only 80% of young people approached consent to take part as found in similar studies (Coulton S et al., 2023) means we would need to approach 702 young people, over the recruitment period. Allowing for a slower start of 20/ per month recruited over the first three months, means 36 will need to be recruited in each month between January 2024 and February 2025, allowing for a six-month follow-up for the interim report submitted in September 2025.

Analysis

All analysis is conducted using STATA 16 SE. Analysis will be conducted and presented in accordance with the CONSORT guidelines. The validity of randomisation will be explored by presenting baseline measures of central tendency and estimates of precision for continuous variables, and proportions for categorical variables broken down by allocated arm and stratification factors for both staff and participant samples.

Primary outcome analysis

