To avoid loss of efficiency missing outcome values will be imputed using multiple imputation, if the proportion of missing data is greater than 5% and less than 40%. Where there is less than 5% missing data, the proportion of missing data is considered negligible and missing observations will be excluded. Multiple imputation methods perform less well when the amount of missing data is substantial, if more than 40% of the primary outcome data are missing for the primary analysis the assumptions are less plausible. The interpretative limitations of the trial data will be discussed in the results section, where this is the case.

An initial variable reduction analysis will explore the relationship between all potentially prognostic baseline covariates and whether a follow-up data point is missing. Only variables where there is an association, p -value > 0.10 , will be included in the imputation model. The

association between the number of imputations will be dependent on the amount of missing data. As a minimum the number of imputations will be derived to ensure at least 96% statistical efficiency (*RE*) according to the formula below, where λ is the fraction of missing values and M is the number of repetitions (eq. 4).

$$RE = \left(1 + \frac{\lambda}{M}\right)^{-1}$$

The statistical model and assumptions made in the analysis of the primary outcome will also be implemented in the multiple imputation procedures. If it is suspected data is missing not at random or the pattern of missing data is associated with trial allocation, sensitivity analysis will be performed using a pattern mixture approach with mixed modelling and multiple imputation to compare the sensitivity of conclusions to varying assumptions about the missing value mechanism.

Intra-cluster correlations (ICCs)

The trial is individually randomised with stratification at the level of service, no ICC's will be calculated.

Compliance

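### Young people are nested within practitioners who each serve one arm, but the sample size and the effect models for young people's outcomes ignore practitioner, so the 80% power and the planned standard errors hold only under conditions the plan does not state.

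*SAP*

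**What the plan says.** **Two linked allocations.** The Protocol (Randomisation) and SAP (Introduction) randomise staff to be trained in RBT or to continue BAU. Young people are randomised separately: "The allocation will involve an equal probability of receiving RBT or BAU". The result is passed to service staff, "who will decide which staff member, matching their allocated intervention or control group, a young person should be assigned to". A randomised practitioner is therefore meant to hold cases from one arm only.

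**Caseload.** Protocol, Sample size calculations: "Each interventionist can manage a harmonic mean of 10 young people through the course of the study". Both documents ask for at least 56 practitioners, 28 per arm. These figures serve as a capacity check only.

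**Sample size.** The SAP states "We have used an effect size difference of 0.25 as an important difference" and, "using a two-sided test, alpha of 0.05 and power at 80% requires 506 young people to be followed-up at our primary endpoint". The rows for ICC, average cluster size and number of clusters are n/a in both sample-size tables.

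**Models.** SAP equations 1 to 3 contain allocation, the baseline value, sex, age group, service dummies and one individual-level error. The CACE equations (SAP, Compliance) have no practitioner term, the per-protocol set is analysed like the ITT set, and multiple imputation reuses the primary model. The Protocol (Analysis) says "We will apply a multi-level model allowing for participants to be nested within services as a fixed effect", which concerns service and not practitioner. On ICCs the SAP says: "The trial is individually randomised with stratification at the level of service, no ICC's will be calculated".

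**The concern.** The SAP's reason for omitting ICCs looks only at the second allocation. Practitioner is tied to arm by the first, so the RBT and BAU means come from two different sets of practitioners. If practitioners differ in the outcomes their young people achieve, that variation enters the treatment contrast, and randomising young people one by one does not remove it. Service dummies take out differences between services but not between practitioners within a service.

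The plan itself gives grounds for expecting such differences. The Protocol (Secondary outcomes) treats therapeutic alliance as a strong predictor of outcome, and the SAP (Further analyses) examines the practitioner's attitude to trauma-informed practice as a predictor.

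At stake are the primary confidence interval and p-value, and what the trial can be said to detect. Because no ICC would be estimated, a reader of the report could not judge how far the primary result was affected.

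**Working it through.** **Inputs from the documents.** Effect size 0.25 (standardised, so SD = 1), two-sided alpha 0.05, power 80%, 253 per arm followed up, 10% loss, 562 randomised. Practitioners: at least 56 needed; 35 + 36 = 71 randomised according to the SAP, which also gives 73 as the number available.

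**Assumed.** The residual practitioner ICC (after service and the other covariates), 0.01 to 0.10; the documents give none. Baseline correlation is zero unless stated, as in the plan's own sample size.

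**Step 1: reproduce the plan's figure.** The t-based two-sample formula gives 252.13 per arm, rounded up to 253, or 506 in all. Power is Phi(0.25 × sqrt(506/4) − 1.96) = Phi(0.852) = 80.3%. For attrition, 506/0.9 = 562.2. The stated figures are therefore those of independent observations, with a design effect of 1.

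**Step 2: analysed cluster size.** m = 506/56 = 9.04 with the minimum number of practitioners; m = 506/71 = 7.13 if all 71 stay.

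**Step 3: formulas.**
- Design effect: DE = 1 + (m − 1) × ICC
- Power of a valid analysis: Phi(0.25 × sqrt(506/(4 × DE)) − 1.96)
- Type I error of the planned test: 2 × (1 − Phi(1.96/sqrt(DE)))
- Minimum detectable effect size (MDES): (1.960 + 0.842) × sqrt(2 × DE/253)
- Baseline correlation that cancels DE: r = sqrt(1 − 1/DE)

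Example at ICC 0.05 with 56 practitioners: DE = 1 + 8.04 × 0.05 = 1.402. Power = Phi(2.375 − 1.96) = 66%. Type I error = 2 × (1 − Phi(1.655)) = 9.8%. r = sqrt(1 − 1/1.402) = 0.54.

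**Step 4: results, 56 practitioners.**

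| Assumed ICC | DE | Power | Type I error | MDES | Offsetting r |
|---|---|---|---|---|---|
| 0 | 1.000 | 80.3% | 5.0% | 0.249 | 0 |
| 0.01 | 1.080 | 77.2% | 5.9% | 0.259 | 0.27 |
| 0.02 | 1.161 | 74.2% | 6.9% | 0.268 | 0.37 |
| 0.05 | 1.402 | 66.1% | 9.8% | 0.295 | 0.54 |
| 0.10 | 1.804 | 55.3% | 14.4% | 0.335 | 0.67 |

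**Results, all 71 practitioners.**

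| Assumed ICC | DE | Power | Type I error | MDES | Offsetting r |
|---|---|---|---|---|---|
| 0.01 | 1.061 | 77.9% | 5.7% | 0.257 | 0.24 |
| 0.02 | 1.123 | 75.6% | 6.4% | 0.264 | 0.33 |
| 0.05 | 1.306 | 69.2% | 8.6% | 0.285 | 0.48 |
| 0.10 | 1.613 | 60.0% | 12.3% | 0.316 | 0.62 |

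**Step 5: simulation check.** With 28 practitioners per arm, 9 young people each and 20,000 runs per setting, the unadjusted test had type I error of 4.9% / 6.2% / 10.1% / 14.8% at ICC 0 / 0.01 / 0.05 / 0.10. A comparison of practitioner means held 4.8% / 5.2% / 5.1% / 4.7%, with power of 79% / 75% / 64% / 54%. The slightly lower power reflects the t reference with few clusters. Under the alternative the unadjusted test rejected in 79% / 77% / 74% of runs at ICC 0.01 / 0.05 / 0.10, but at an inflated alpha.

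**The case against.** **The ICC is unknown.** A reader might infer that the trial does not have 80% power and that its standard errors are wrong. The documents do not support that as a fact, because both statements need a positive residual ICC and none is given. At ICC 0.01 the effect is small: power 77% to 78%, type I error just under 6%. Service dummies also remove between-service variation, so only the within-service ICC counts. This stands, and the point is conditional.

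**The plan left slack.** Both documents deliberately omit the baseline correlation from the sample size, while equation 1 adjusts for baseline SRDS. That could restore power in full (last column of each table). It stands for power. It does not correct type I error if practitioner variance remains after adjustment.

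**Not all models are affected.** A reader might extend the point to every model in the SAP. Staff outcomes are analysed at practitioner level, so this clustering does not arise there. The SAP (Missing data) also mentions mixed modelling in a sensitivity analysis, without saying at what level.

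**The cluster inputs are not the expected design.** Ten per practitioner is a capacity and 56 a floor; with 71 practitioners, 562/71 is about 8 randomised each. Hence both scenarios above.

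**The structure is less tidy than one practitioner per case.** In Youth Justice, staff already trained in RBT are not randomised and are excluded only from control cases. Tier 2 and 3 work is led by trauma leads or a psychologist, in the RBT arm only. This complicates the definition of the cluster. It does not argue for ignoring it.

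**Conclusion.** The omission is established by the documents: practitioner is nested in arm by design, no specified effect model for young people's outcomes includes it, and individual randomisation of young people is not a valid reason to leave it out.

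Its size is not established. The 80% power holds only if the residual practitioner ICC is zero or baseline adjustment offsets it, and the planned intervals are too narrow whenever that ICC is positive. Over the assumed range 0.01 to 0.10, with no baseline correlation, power runs from 77% down to 55% with 56 practitioners and from 78% down to 60% with 71. Type I error runs from about 6% to 14% with 56 and from about 6% to 12% with 71. The calculation assumes equal cluster sizes and the same ICC in both arms.

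This should be corrected before analysis. The power question may turn out to be minor, but the validity of the primary test should not rest on an unexamined assumption of zero practitioner variation.

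**What to change.** 1. **Primary and secondary models.** Add to equations 1 to 3 a random intercept for the first-assigned practitioner, or practitioner-clustered standard errors, with a small-sample correction. Keep service, sex, age group and the baseline value as fixed effects.
2. **Dependent analyses.** Carry the same structure into the imputation, CACE and per-protocol models.
3. **Define the practitioner unit** for Youth Justice cases held by already-trained, unrandomised staff, and for Tier 2 and 3 cases led by a trauma lead or psychologist.
4. **ICC section.** Replace the statement that none will be calculated with a commitment to report the practitioner ICC.
5. **Sample-size tables.** Replace the n/a cluster rows with the expected practitioners per arm and analysed cluster size, over 56 to 71 practitioners in total. Reconcile the SAP's 73 with 35 + 36 = 71.
6. **Power.** Restate power or MDES over ICC 0.01 to 0.10 with an explicit baseline correlation.

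**Cost.** SAP wording and one extra model term. The Protocol (Compliance) says the shared system already records the staff member for planned meetings, so no new collection from young people should be needed. The downside is that the stated power and MDES become less favourable.

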### **Compliance**

As interventions are personalised to the young person's needs across both the RBT and BAU groups, compliance and dose will be assessed from two perspectives. From a staff perspective we will assess fidelity to the components of the allocated tier in the RBT arm (case formulation, multi-agency meetings, reviews). For participants, the dose will be assessed in both arms as the proportion of planned meetings attended. Interactions between young people and staff are recorded on the same system between the different participating services. Records include planned meetings, who leads the meeting, staff member, trauma lead or psychologist and attendance. Compliance will be categorised into 5 quintiles, 0-19%, 21-40%, 41-60%, 61-80% and 81-100%. These will be employed in a dose response analysis. In addition, we will use this data to augment the micro-costing of the intervention.

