A secondary analysis, a Complier Average Causal Effects (CACE) model, will be conducted using an instrumental variable framework. CACE analysis allows us to avoid bias by weighting the ITT treatment effect by the dose of intervention or control treatment received, as a proportion of what was offered. This provides an unbiased estimate of the role of dosage in the outcomes observed. Compliance will address the extent to which those in the intervention group received the different elements of their allocated tier. By incorporating different quintile thresholds of dose, we can explore the nature of the relationship between compliance, dose, and outcomes observed.

In addition to this we would want to explore whether certain factors are associated with non-compliance to identify potential clusters of participants who do not comply. We will conduct a latent class analysis to identify clusters associated with non-compliance. This will enable an exploration of whether there are groups of participants who are harder to reach than others and by augmenting this quantitative approach with targeted qualitative interviews with young people and interventionists, enable the wider research group to explore what adaptations may be necessary to increase accessibility and compliance.

An aspect of our qualitative work with key stakeholders involves examining participants' positive and negative experiences of the allocation to different tiers of the intervention, exploring how these perspectives concur with those who conduct the trauma screening and allocate the participant to a tier, to explore at what points negative and positive experiences are at their greatest and what steps could be taken to ameliorate these experiences to improve the delivery and acceptability of the intervention. This information will be elicited as part of the semi-structured interviews.

The mechanism of change will be explored using a mediation model approach. Exploring factors that impact on the mechanism of change will be assessed using regression analysis to model the relationship between pre-randomisation factors and observed outcomes at 6 months. Interaction terms with allocation arm will be included in the analysis, and a significance level of 0.1 will be used to determine which factors are included in the regression model. Pre-randomisation factors include sex, age, ethnicity, IMD decile, number of adverse child experiences and family cohesion.

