To explore the role of compliance on outcomes we will conduct a Complier Average Causal Effects analysis (CACE). The definition of compliance with allocation for this trial is as follows (see Table 1 below): (i) those who receive trauma screening (TS) and 80% of RBT interventions offered will be considered 'compliers' in the intervention group (cell A); (ii) those in the control group who did not receive any RBT intervention (cell D). In the intervention group, those attending no trauma screening and/ or less than 80% of interventions offered will be considered 'non-compliers', (cell B). All non-compliers in the intervention group are regarded as being 'contaminated' because they received the control condition (no RBT interventions). For the control group, there is no option for control participants to access the intervention, so there cannot be non-compliance hence this is n/a (cell C).

To further explore the role of compliance on outcomes we will create several thresholds for intervention compliance;

1. TS versus no TS.
2. TS and/ or < 20% of RBT interventions versus TS and >= 20% RBT.
3. TS and/ or < 40% of RBT interventions versus TS and >= 40% RBT.
4. TS and/ or < 60% of RBT interventions versus TS and >= 60% RBT.
5. TS and/ or < 80% of RBT interventions versus TS and >= 80% RBT.

CACE analysis will be undertaken for each threshold and presented as a sensitivity analysis to allow a comparison of outcomes, (RBT group vs BAU) at different thresholds of compliance.

Table 1: Compliance/non-compliance according to group allocation versus intervention received.

	Actually received...	
Allocated to... ↓	Intervention	Control
Intervention	
A. Intervention complier
 
Meeting the stated threshold
	
B. Intervention non-complier
 
Not meeting the stated threshold

Control	
C. Control non-complier
 
n/a
	
D. Control complier
 
Control group participant

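### CACE at the attendance thresholds counts part-treated participants as untreated, so the estimate grows with the threshold by arithmetic and cannot show a dose-response

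*SAP*

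**What the plan says.** SAP, Compliance, defines an RBT-arm complier as someone who has trauma screening (TS) and 80% of the RBT interventions offered. Everyone else in that arm is a non-complier and is described as contaminated "because they received the control condition (no RBT interventions"). For controls the SAP states: "For the control group, there is no option for control participants to access the intervention, so there cannot be non-compliance". Cell C of its compliance table is therefore marked not applicable.

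CACE is then repeated at five nested thresholds: TS alone, then TS with at least 20%, 40%, 60% and 80% of RBT. The second is worded "TS and/ or < 20% of RBT interventions versus TS and >= 20% RBT". The series is labelled a sensitivity analysis. Equation 5 sets CACE equal to ITT divided by the proportion compliant. Equations 6 and 7 give the two-stage version, with allocation as instrument and no covariates.

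The protocol goes further. Its Compliance section plans to use attendance bands in a dose-response analysis. Its Research Methods section (implementation and process evaluation) uses CACE at several dose thresholds to study how dose relates to outcome, and says: "This provides an unbiased estimate of the role of dosage in the outcomes observed". On control exposure, Protocol, Analysis, says of the primary model: "nor can we adjust for any potential contamination due to multi-agency working".

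**The concern.** Dividing ITT by the proportion compliant gives a complier effect only if allocation does nothing for non-compliers. Here the non-compliers include young people who were screened, had a trained worker and attended most of their sessions. Any benefit they had is in the ITT numerator but is credited wholly to those above the threshold. The SAP recognises the distinction elsewhere: its per-protocol paragraph separates those who partly complied from those who did not receive the intervention.

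The threshold series is exposed to a second problem. Its numerator never changes and its denominator shrinks, so a rising set of estimates is guaranteed once the ITT is non-zero and attendance varies. Laid out by threshold, this looks like evidence that more RBT works better. Implementation conclusions about dose could rest on it.

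**Working it through.** **Inputs.** From SAP, Sample size calculations overview: "We have used an effect size difference of 0.25 as an important difference" and "using a two-sided test, alpha of 0.05 and power at 80% requires 506 young people to be followed-up at our primary endpoint", 253 per arm. The documents give no compliance rate, so every proportion below is an assumption. Effects are shown as magnitudes in SD units.

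**The plan's own figure.** The normal formula n = 2(1.96 + 0.8416)²/0.25² gives 251.2, so 252 per arm. The t-test version gives 252.13, so 253 per arm and 506 in total. Then 506/0.90 = 562.2, in line with the stated 562. The 0.25 SD used below is thus the plan's own target effect.

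**Step 1: what eq. 5 estimates.** Let p be the proportion at or above the threshold, a the mean effect in that group and b the mean effect below it, with no control exposure. Then

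ITT = p·a + (1 − p)·b, so CACE = ITT/p = a + b(1 − p)/p.

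The exclusion restriction is b = 0. If part-treated participants benefit at all, the excess is b(1 − p)/p: b/3 at p = 0.75, b at p = 0.50 and 3b at p = 0.25. With one binary instrument, no covariates and no control receipt, equations 6 and 7 reduce to the same ratio.

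**Step 2: the series with ITT = 0.25.**

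| Assumed proportion meeting thresholds 1 to 5 | CACE | Last/first |
|---|---|---|
| 0.98, 0.95, 0.90, 0.85, 0.75 | 0.255, 0.263, 0.278, 0.294, 0.333 | 1.31 |
| 0.95, 0.90, 0.80, 0.65, 0.50 | 0.263, 0.278, 0.312, 0.385, 0.500 | 1.9 |
| 0.85, 0.75, 0.60, 0.40, 0.25 | 0.294, 0.333, 0.417, 0.625, 1.000 | 3.4 |

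Nothing about dose and outcome entered these figures.

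**Step 3: can the series tell dose-response from none?** The check simulated 4,000 trials of 253 per arm, with assumed compliance of about 95, 91, 78, 58 and 30%.

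- Flat effect (0.25/0.95 = 0.263 for anyone screened, at any attendance): mean CACE 0.26, 0.27, 0.32, 0.43, 0.82.
- Linear effect (0.4 × dose): mean CACE 0.26, 0.27, 0.32, 0.43, 0.82.
- No effect: mean about 0 at every threshold, with rejection at 4.3 to 4.7%.

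The first two series are the same to two decimals. In the flat case the 80% threshold overstates the effect 0.82/0.263 = 3.1 times, while threshold 1 recovers it. In the linear case the true effect above 80% attendance lies between 0.4 × 0.8 = 0.32 and 0.40, so 0.82 is at least twice too large. The size of CACE never fell with the threshold in any simulated trial. Standard errors also scale with 1/p, so power barely moves (79.6% to 78.7% in the flat case).

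**Step 4: control exposure.** Take a true effect of 0.263 and 95% screened, with an assumed 5, 10 or 20% of controls exposed. ITT becomes 0.263 × (0.95 − pC) = 0.237, 0.224 or 0.197. The SAP's threshold 1 then gives ITT/0.95 = 0.249, 0.235 or 0.208. Dividing by (0.95 − pC) returns 0.263 each time. Ignoring control exposure makes CACE too small.

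**The case against.** The SAP keeps ITT as the primary analysis, presents the thresholds as a sensitivity analysis, and says openly that CACE enlarges the effect when compliance is imperfect. Its first threshold, TS versus no TS, is already close to a valid contrast. The 80% definition would also be right if benefit arose only at 80% attendance or more: simulated with a true 0.5 in that group alone, the 80% CACE was 0.49. The process evaluation's named method for its dose question (IPE Q4) is a stratified regression with confounder control, not CACE alone. All of this stands, and it limits the consequences. It does not rescue the series, because the documents do not argue that attendance below 80% is inert and the protocol claims unbiasedness without that condition.

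A reader might infer more than the documents support:

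- *That assuming unexposed controls adds to the inflation.* It works the other way (Step 4).
- *That the method produces a dose-response when RBT does nothing.* Under a true null, expected CACE is zero and type I error holds. A chance ITT is still fanned out, but half the time as benefit and half as harm. The false gradient is systematic only when ITT is non-zero and dose is irrelevant.
- *That the protocol expects contamination.* It allows for the possibility. It also has young people assigned to staff of their own arm, and in Youth Justice sends controls only to untrained staff.
- *That a trauma lead's response to distress at an assessment is RBT exposure.* It is described as a response to possible re-traumatisation, and nowhere called RBT.

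Omitting covariates from equations 6 and 7 costs precision but does not bias the ratio under randomisation. The threshold wording is a slip: the main definition in the same section correctly refers to no trauma screening.

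**Conclusion.** The point holds for the 80% definition and the other partial-attendance thresholds. Coding partial receipt as none breaks the exclusion restriction wherever partial attendance has any effect. The non-decreasing series follows from eq. 5 and needs no assumption about dose, so it cannot support the dose-response use or the unbiasedness claim.

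The size depends on compliance, which is unknown. With ITT at 0.25 SD, the 80% CACE is 0.33, 0.50 or 1.00 at 75, 50 or 25% compliance, and no single multiple should be quoted as the error. Effect size is at risk rather than significance. The primary ITT result is untouched, so this should be corrected but does not threaten the trial's main conclusion.

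A separate point runs in the opposite direction: the SAP's statement that control non-compliance cannot occur conflicts with the protocol's acknowledgement of potential contamination. If any controls received RBT, the planned denominator is too large and CACE is biased toward zero.

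**What to change.** 1. Make any RBT receipt (trauma screening completed or any RBT session) the main CACE contrast in place of the 80% definition. Threshold 1 needs little change to become this.
2. Drop the threshold series, or keep it with a statement that it is not evidence of dose-response.
3. Delete the sentence claiming unbiasedness for dosage from Protocol, Research Methods.
4. Put the eq. 1 covariates in both 2SLS stages.
5. In thresholds 2 to 5, change the opening words of the lower group to no TS and/or, so that the groups do not overlap.
6. Fill cell C from data and use ITT/(pA − pC). Protocol, Compliance, says of the system shared by the services: "Records include planned meetings, who leads the meeting, staff member, trauma lead or psychologist and attendance". Count defined RBT components only: trauma screening, RBT case formulation or mapping, and delivery by an RBT-trained worker. Do not count any contact with a trauma lead. Those leads include service managers and the staff who assess need at referral, so routine contact would inflate pC and hence CACE.
7. If continuous dose is also reported, state the linearity assumption and define RBT dose for controls, who have no planned RBT contacts. This is not a cure: with a flat effect and an assumed mean dose of 0.6, it gives 0.25/0.6 = 0.42 per full dose against a true 0.26.

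The cost is SAP edits, one protocol edit, and a written rule for coding RBT exposure from the service records, with the extraction to apply it. No new participant data collection is planned for, provided those records identify the listed components.
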